 - Staged with a planned return for reoperation (such as but not limited to damage control laparotomy or burns surgery) OR
 - Change in operative plan such that during the first procedure it is determined that a reoperation is necessary, even if the patient was enrolled preoperatively
- **Return to theatre:** Each individual patient should only be included in the study *once*. Patients returning to theatre due to complications following earlier surgery can be included, as long as their indexed procedure has not already been included in the CASCADE audit.

You should collect data on consecutive patients operated at your centre during the data collection period. This means that all eligible patients should be included.

Strategies to identify consecutive eligible patients could include:

- *Daily review of elective theatre lists.*
- *Daily review of handover sheets/ emergency admission and ward lists.*
- *Daily review of theatre logbooks (both elective and emergency).*

6. Covariates:

Data will be collected on audit standards and confounding factors for risk-adjusted analyses. These include age, sex, ethnicity, body mass index, American Society of Anaesthesiologists (ASA) grade, relevant comorbidities, smoking status, anticoagulant or antiplatelet use, preoperative blood test values, and preoperative anaemia management. Variables including operative urgency, operative procedure, operative contamination, use of tranexamic acid, intraoperative blood transfusions used, haemoglobin level at transfusion, duration of procedure and post-operative iron therapy will also be collected. Without appropriately adjusting for risk factors, it is likely that any findings would be biased and unable to be appropriately analysed on a national scale. A full list of required data fields is available in **Appendix B**, and on the REDCap database.

7. Outcome Measures and Follow-up:

Primary outcome measure:

- Rates of compliance to pre-, intra-, and postoperative audit standards in reducing risk of postoperative cardiovascular complication.

Secondary outcome measures:

- Incidence of postoperative cardiovascular complications within 30-days of surgery according to the Standardized Endpoints for Perioperative Medicine (StEP) cardiovascular.¹³ (see **Appendix D: Definitions of Key Outcomes**).
- 30-day postoperative blood transfusion rates
- 30-day complication rates defined according to the Clavien-Dindo classification (see **Appendix D: Definitions of Key Outcomes**)

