REDCap accounts will not be issued until evidence is sent to your university's regional lead that the following approvals are in place at your centre:

- *Successful registration of CASCADE with the audit department.*
- *Caldicott Guardian permission for data to be submitted to REDCap.*

11. Quality assurance:

Design: This protocol was written with guidance from an expert cross-speciality advisory group.

Training: CASCADE Regional Leads are encouraged to hold local meetings with collaborating teams at their medical school to brief them on the protocol, and to feedback any local issues or questions raised. To ensure collaborators understand the study topic, inclusion criteria, primary outcomes, application of the Clavien-Dindo classification and the principles of data governance, they will all be asked to complete online **e-learning** on these (pass mark is 100%) prior to starting data collection (online at: <https://incept.ac.uk/course/view.php?id=7>).

Project team structure: Medical students will take the lead in disseminating and delivering this study alongside junior doctors. These 'mini-teams' should be supervised by up to two consultants (two surgeons or anaesthetists) at each site in the UK & Ireland, and by a consultant per surgical specialty in the rest of Europe (**Figure 1**). Each team should include at least one qualified doctor to provide additional local support for participating medical students.

[figure not shown]

Figure 1: STARSurg “Mini-team” structure, roles, and responsibilities.

Data completeness: Following data collection, only data sets with >95% data completeness will be accepted for pooled national analysis. To emphasise the importance of data completeness to collaborators, data collection periods with >5% missing data points will be excluded from the study and collaborators from those periods withdrawn from the published list of citable collaborators.

Validation: This methodology for student-driven snapshot audit has been widely validated across multiple datasets, both nationally in the UK and Ireland and internationally, demonstrating high levels of case ascertainment (typically greater than 90 to 95%) and data accuracy (greater than 96 to 98%).^{29,30}

12. Authorship:

In accordance with National Research Collaborative (NRC) authorship guidelines³, all research outputs from CASCADE will be listed under a single corporate authorship (“STARSurg Collaborative & EuroSurg Collaborative”).

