 - Sponsorship of local audit registration, and responsible to ensure local collaborators act in accordance with local governance guidelines.
 - Inclusion of at least one data collection period at their centre which meets the criteria for inclusion within the CASCADE dataset.
 - Facilitation of local audit results presentation and support of appropriate post-audit interventions.
 - Completion of workplace-based assessments for students or trainees

(ePortfolio/ISCP), if requested.

Criteria for centre inclusion within CASCADe:

- Obtain of all appropriate local approvals for conduct of the CASCADe audit.
- Successful completion of at least one data collection period at the centre (with a minimum of one eligible patient per period included). Individual data collection periods will only be included when:
 - i. >95% data completeness has been achieved.
 - ii. All data for the period has been uploaded within the specified deadlines.

Please note if these criteria are not met, then the contributing mini-team and/or the centre may be removed from the dataset and authorship list (please get in contact as soon as potential issues arise so we can support as many centres to be included as possible). See **Appendix F** for advice to help ensure for successful inclusion of your centre in the CASCADe audit.

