10. Regularly follow-up for information on complications over the 30-day post-operative period. This study is prospective, so you should not wait until the end of the post-operative period to

follow-up patients (this would be retrospective). Discuss the best way to follow up patients with the consultant supervising your audit, as this will vary from centre to centre.

Be proactive in identifying post-operative adverse events, as this will prevent under-estimation of true complication rates. Remember that in this audit no changes to normal patient follow-up should be made.

Strategies for identifying complications in the follow-up period include:

- *Regularly reviewing patient notes to identify in-hospital complications.*
- *Reviewing clinic notes and clinic letters, if seen in clinic by 30 days.*
- *Checking electronic systems and handover lists for re-admissions.*
- *Checking for A&E re-attendances.*

If case notes are reviewed shortly prior to discharge they do not need to be requested/retrieved again for follow-up at 30-days, but do check electronic records for discharge letters, clinic letters, re-admissions.

11. Ensure all data has been uploaded to the REDCap system by the data collection deadline, and you have completed all fields, avoiding missing data points. If more than 5% of patients at your centre have missing data, your centre cannot be included in the CASCADE dataset and your name will be withdrawn from the author list.
12. It is a condition of participation in CASCADE that following completion of the audit at your centre you must ensure that your local results are presented to your hospital's surgical department and/or reported back to the audit department. You may also like to return to present again at a later date, when the final national results of CASCADE become available.

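### Inclusion and authorship depend on completeness of entered records only, and no count of eligible patients is required, so selective omission can bias compliance and incidence without being seen

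*Protocol*

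**What the plan says.** The completeness rule appears in three places in the protocol.

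- **Section 11, Data completeness:** "data collection periods with >5% missing data points will be excluded from the study", with "collaborators from those periods withdrawn from the published list of citable collaborators".
- **Section 12, criteria for centre inclusion:** a period counts when ">95% data completeness has been achieved" and its data are uploaded on time, "with a minimum of one eligible patient per period included". Local approvals are also needed. No criterion concerns the share of eligible patients captured.
- **Appendix E, step 11:** "If more than 5% of patients at your centre have missing data, your centre cannot be included in the CASCADE dataset". Here the unit is patients per centre, whereas section 11 counts data points per period.

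On who must be entered, section 5 tells teams to collect consecutive patients: "This means that all eligible patients should be included". It then lists ways in which teams could find them, among them "Daily review of theatre logbooks (both elective and emergency". These are suggestions, and no resulting count has to be reported. The fields in Appendices A and B are all patient-level.

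The Validation paragraph of section 11 describes this audit method as tested in earlier datasets, "demonstrating high levels of case ascertainment (typically greater than 90 to 95%) and data accuracy". It plans no such measurement in CASCADE.

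**The concern.** A missing data point can exist only for a patient who has been entered. A team close to the limit can improve its result by finding the missing items or by not entering the patient. Only the first is what the protocol wants, but the rule treats both alike, and authorship depends on the result. No deliberate conduct is needed: giving up on a patient whose notes are hard to trace has the same effect.

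This touches the primary outcome directly. Pre-operative audit standard 1 is that weight and BMI are recorded. Appendix B lists BMI as a numeric field with no option for not recorded. For that standard, an absent BMI is both the non-compliance being audited and a missing data point that counts against the team.

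If omitted patients differ from those entered, compliance and 30-day incidence shift. A larger sample does not remove the shift, and without a denominator nobody can see it. A statistical analysis plan cannot supply the count later. Section 8 also asks for paper copies to be destroyed after upload, which makes it harder to rebuild.

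**Working it through.** **Inputs from the protocol.** Section 9 gives about 300 centres and ten patients per centre per week; section 1 gives 14 days. So 300 × 10 × 2 = 6000, which reproduces the anticipated sample, and 10 × 2 = 20 patients per centre per period. Appendix B has 23 + 12 + 15 = 50 numbered items. Items 19, 20 and 21 alone hold 3, 7 and 3 values, so 50 data points per patient is a working assumption on the low side. Section 11 cites ascertainment typically above 90 to 95%, so below 5 to 10% missed: a ceiling from earlier audits, not an estimate for this one.

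**Assumptions.** True incidence 8%; risk in omitted patients 1 to 3 times that in entered patients; 2% missed as a milder case; true compliance 80%.

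**The incentive, Appendix E rule.** Take a centre with one period of 20 patients, two with any missing data: 2/20 = 10%, excluded. Leave both out: 0/18 = 0%, accepted.

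**The incentive, section 11 rule alone.** Suppose 18 patients miss 1 item each and 2 miss 20 each: (18 × 1 + 2 × 20)/(20 × 50) = 58/1000 = 5.8%, excluded. Leave the two out: 18/(18 × 50) = 18/900 = 2.0%, accepted. This example would still fail Appendix E, because all 18 remaining patients have something missing.

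In both examples ascertainment is 18/20 = 90%, and no field in Appendix A or B would show it.

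**The two rules disagree.** If two of 20 patients each miss one item, section 11 gives 2/1000 = 0.2% (accepted) and Appendix E gives 2/20 = 10% (excluded).

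**Possible bias in incidence.** With fraction m missed and relative risk r, observed incidence = p/(1 − m + r·m), where p = 8%.

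| m | r | Observed | Bias (points) |
|---|---|---|---|
| any | 1 | 8.00% | 0 |
| 2% | 2 | 0.08/1.02 = 7.84% | −0.16 |
| 5% | 2 | 0.08/1.05 = 7.62% | −0.38 |
| 10% | 3 | 0.08/1.20 = 6.67% | −1.33 |

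The simple 95% half-width is 1.96 × √(0.08 × 0.92/6000) = 0.69 points. With 20 patients per centre and an assumed intracluster correlation of 0.05, the design effect is 1 + 19 × 0.05 = 1.95, and the half-width is 0.69 × √1.95 = 0.96 points.

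**Possible bias in compliance.** Observed compliance = (p − m·q)/(1 − m), where q is compliance among omitted patients and p = 80%.

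- q = 80%: 80%, no bias.
- q = 50%: (0.80 − 0.025)/0.95 = 81.6% at m = 5%; (0.80 − 0.05)/0.90 = 83.3% at m = 10%.
- q = 0, as when the omitted patients are those with no BMI: 0.80/0.95 = 84.2% and 0.80/0.90 = 88.9%.

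The simple half-width is 1.96 × √(0.80 × 0.20/6000) = 1.0 point.

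**The case against.** The protocol has relevant controls. Section 5 requires every consecutive eligible patient. Collaborators must pass e-learning, including a patient-selection module, at 100%. Consultants supervise, and local results must be presented at the hospital. The one-patient minimum in section 12 is a floor for a period to count and does not waive section 5. Many fields accept None or Not available, and absent pre-admission bloods are entered as 0, so poor notes often create no missing point. Patients with long complicated stays remain visible on the ward and handover lists that section 5 suggests reviewing daily.

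All of this stands, and it weakens the incentive. None of it measures ascertainment, and the softer entry options do not cover BMI.

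A reader might go further and infer that every rate in CASCADE is biased, that teams will choose whom to enter, or that 5 to 10% of patients will be missed. The documents support none of these. The bias is zero if omitted patients resemble those entered, nothing shows that teams behave this way, and the cited ascertainment puts missed cases typically below that range.

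It is also fair to say that a count reported by the same team, with the same authorship interest, can leave out the same patients. The fix has to allow for that.

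**Conclusion.** The point holds as a weakness in data collection. A stated rule penalises entering poorly documented patients, the instruction to include everyone is not checked, and ascertainment is borrowed from earlier audits. Omission can therefore bias compliance and incidence without being seen.

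The size cannot be known from the protocol. On the assumptions above, the bias in incidence runs from zero to about 1.3 points. It is below the simple half-width of 0.7 points in the milder cases and above it, even allowing for clustering, only in the most extreme one. Compliance with a documentation standard could move further, by up to 8.9 points if 10% of patients were missed and none of them complied. These figures bound a possibility and do not predict a bias. Separately, sections 11 and 12 and Appendix E must be reconciled, since the same data can pass one version of the rule and fail another.

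**What to change.** In section 11, require one figure per team per period: the number of eligible operations for its specialty group in the 14 days, from theatre logbooks or lists. Take it from the theatre system where possible, or have it confirmed by the supervising consultant already in place, so that it does not rest on the data-collecting team alone.

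Report entered/eligible as CASCADE's own ascertainment, in place of the figure from earlier audits. Repeat the compliance and incidence analyses where ascertainment is high, for example at least 95%. Pool by centre for this: 19/20 is exactly 95%, so a team with fewer than 20 eligible patients falls below it on a single omission.

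State one unit for the completeness rule and use it in sections 11 and 12 and Appendix E.

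The cost is one REDCap number and a short count per team, in which the eligibility exclusions have to be applied, plus a sentence in section 11 and one sensitivity analysis. The ascertainment figure may prove less favourable than the one now cited. A count reported by the team reduces the problem but does not remove it.

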Appendix A: Summary of data fields

Use with Appendix X (Data Dictionary) to aid data collection.

				REDCap Unique ID					
Section 1: Pre-operative data fields									
Age	___(years)	Gender	 Male  Female	ASA grade	 I  II  III  IV  V	BMI	___ . ___ (2dp)		
Smoking status	 Current (≤ 6 weeks)  Current (> 6 weeks)  Ex-smoker  Never smoked			Clinical Frailty Scale	 1-3  4-6  7-9	https://bit.ly/3c9ve3d			
Hx of cardiovascular disease (Tick all that apply)	 MI  Angina  TIA/stroke  Hypertension  Atrial Fibrillation  VTE  Pulmonary Embolism  Congestive Heart Failure (CHF) (If CHF: NYHA:  I  II  III  IV)			Hx of respiratory disease	 Exertional dyspnoea or CXR (mild COPD)  Exertional dyspnoea < 1 flight or CXR (moderate COPD)  Dyspnoea at rest/rate > 30 at rest or CXR (fibrosis or consolidation)  None	Hx of COPD	 Yes  No		
Hx of chronic kidney disease	 I  II  IIIa  IIIb  IV  None	Hx of liver cirrhosis	 Yes  No	Hx of diabetes mellitus	 Type I  Type II (diet / tablet / insulin?)  None	Active cancer and/or cancer treatment	 Yes  No		
IBD	 Yes  No			Hx of VTE	 Yes  No				
Management of iron-deficiency anaemia (IDA) (Tick all that apply)	 None  Pre-operative iron supplementation  Tranexamic acid (TXA)  RBC transfusion (if RBC:  1  2  3  4  ≥ 5 units)			Preop tx (Tick all that apply)	 Aspirin  ACEi/ARB  β -blocker  α_2 agonist  Rate controlling CCB  DHP CCB  None	If preop tx, medication stopped preop?	 Yes, preop  Yes, preop & postop  No		
Preoperative therapeutic anticoagulation				 LMWH  Warfarin  DOACs  None					
Pre-admission blood tests* (Please complete all) *Include blood tests within the 90 days prior to operation				Hb ___ g/L Albumin ___ g/L Creatinine ___ ml/min					
Admission blood tests* (Please complete all) *Include the first blood test results from this admission				Hb ___ g/L WCC ___ $\times 10^9/L$ (1dp) Albumin ___ g/L Sodium ___ mmol/L Potassium ___ mmol/L (1dp) Urea ___ mmol/L Creatinine ___ ml/min					
Admission observations				Pulse ___ bpm Systolic BP ___ mmHg GCS ___ (/15)					
Pre-operative assessment				(If elective)  Yes (pre-admission anaesthetic assessment clinic)  No (If yes: Did this include pre-operative cardiopulmonary exercise testing?  Yes (VO_2 peak ___ mlmin $^{-1}kg^{-1}$ / AT ___ mlmin $^{-1}kg^{-1}$)  No (If emergency)  Yes (inpatient perioperative or elderly medicine)  No					
Preoperative investigations (Tick all that apply)				 ECG (normal / abnormal?)  ECHO (LVEF ___ %)  Coronary angiogram  None					
Section 2: Intra-operative data fields									
Prior operations	 1  2  > 2	Urgency (NCEPOD)	 Elective  Urgent  Expedited  Immediate	Primary indication	 Benign  Primary Malignancy only  Nodal Metastases  Distant Metastases				
Operation	See REDCap and Appendix C for list of operation types (select all that apply)								
Approach	 Open  Laparoscopic  Laparoscopic-assisted  Laparoscopic \rightarrow open  Robotic  Robotic \rightarrow open	Operative Contamination	 Clean  Clean-contaminated  Contaminated  Dirty	Peritoneal soiling	 Serous fluid  Localised pus  Free content  None	WHO checklist	 Yes  No		
Duration of operation	___ mins	Estimated blood loss	___ ml	Intra-operative interventions	 TXA  RBC  None	If RBC, how many units?	 1  2  3  4  ≥ 5	If RBC, Hb at transfusion	 ___ g/L  Not available
Section 3: Post-operative data fields									
Critical care admission	 No  Yes, planned from theatre  Yes, unplanned from theatre  Yes, unplanned from ward If yes, CVC inserted?  Yes  No	Critical care bed days	___ days	Postop Hb	 ___ g/L (day 0-1)  ___ g/L (day 1-3)  ___ g/L (day 4-6)  ___ g/L (prior discharge)  Not available	IDA mx (Tick all that apply)	 None  Iron supplementation  TXA  RBC transfusion (if RBC:  1  2  3  4  ≥ 5 units)		
30-day Follow-up									
Cardiovascular complications within 30 days (Tick all that apply)	 None		Bleeding complication within 30 days		 Clinical non-major bleeding  Major bleeding  None				
	 Myocardial infarction  Myocardial injury  Non-fatal cardiac arrest  Coronary revascularisation		Post-operative length of stay		___ days  None				
	 PE (symptomatic non-fatal / asymptomatic)  DVT (proximal / distal; if either symptomatic / asymptomatic)		Highest 30-day complication grade		___  I  II  III  IV  V (if V: Cardiac / PE / noncardiac?)				
			30-day Reoperation		___  Yes ___  No				
			30-day readmission		 No  Yes(planned/unplanned?)				

	 New onset AF  Stroke				If yes: what was grade of complication:  None  I  II  III  IV  V
30-day postoperative COVID status	 None  Yes, preop  Yes, postop <hr style="border-top: 1px dashed black;"/> If preop: Symptomatic?  Yes  No If preop: Vaccinated?  Partial  Full  No	If readmission, what was Hb	 ___g/L  Not available	If readmission, anaemia intervention	 None  Iron supplement (Oral / IV ?)  RBC transfusion (if RBC:  1  2  3  4  ≥5 units)
Postoperative outpatient VTE prophylaxis duration	___ days	Postoperative outpatient VTE prophylaxis			 None  LMWH  Warfarin  DOACs (if DOAC:  dabigatran  rivaroxaban  apixaban  edoxaban  betrixaban)

Appendix B: Data Dictionary

Pre-operative Data Fields	Required data (definition / comment)	Suggested source(s)
1. Patient age	Years (whole years at the time of operation)	– Clinical letters / notes
2. Patient sex	Male / Female	– Clinical letters / notes
3. Patient body mass index (BMI)	kg/m² (record to two decimal places)	– Drug charts – Clinical letters / notes
4. Patient ASA grade	Grade I-V (Full ASA classification available at: https://www.asahq.org/resources/clinical-information/asa-physical-status-classification-system)	– Anaesthetic notes
5. Smoking status	Current (≤6 weeks, >6 weeks), Previous, Never	– Admissions clerking – Clinical notes
6. Clinical Frailty scale	1-3 / 4-6 / 7-9 (Full Clinical frailty scale available at: https://www.dal.ca/sites/gmr/our-tools/clinical-frailty-scale.html)	– Admissions clerking – Clinical notes
7. History of cardiovascular disease	Yes (myocardial infarction, angina, congestive cardiac failure, TIA/stroke, hypertension, peripheral vascular disease, atrial fibrillation, VTE, pulmonary embolism) / No If congestive cardiac failure, what is the NYHA: I / II / III / IV	– Admission clerking – Anaesthetic notes – Outpatient letters
8. History of respiratory disease	None / Dyspnoea on exertion or CXR (mild COPD) / Dyspnoea limiting exertion to <1 flight or CXR moderate COPD / Dyspnoea at rest/rate >30 at rest or CXR (fibrosis or consolidation)	
9. History of COPD	Yes / No	
10. History of chronic kidney disease	Yes (I / II / IIIA / IIIB / IV / V) / No	
11. History of liver cirrhosis	Yes / No	
12. History of diabetes mellitus	Yes - Type I / Yes - Type II (diet controlled, tablet controlled, insulin controlled) / No	
13. Active cancer and/or cancer treatment	Yes / No	
14. Inflammatory bowel disease	Yes / No	
15. Previous history of VTE	Yes / No	
16. Management of iron-deficiency anaemia	None / Preoperative iron supplementation / Tranexamic acid / RBC transfusion (If yes: 1, 2, 3, 4, ≥5 units)	
17. Preoperative treatment	Yes (Aspirin, ACEi/ARB, β-blocker, α ₂ agonist, rate controlling CCB, DHP CCB) / No If yes, was medication stopped preoperatively? (No / Yes, stopped preop only / Yes, stopped preop & postop)	– Clinical letters / notes PACS software
18. Preoperative therapeutic anticoagulation	Yes (Low Molecular Weight Heparin (LMWH), Warfarin, Direct acting oral anticoagulants (DOACs)) / No	– Clinical letters / notes PACS software
19. Pre-admission blood tests	Haemoglobin (grams / litre) / Albumin (grams / litre) / Creatinine (ml / min) *Include blood tests taken within the 90 days prior to operation. If multiple blood tests have been taken during this period, record the lowest value. If no pre-admission blood tests are available, please record this as 0.	– Pathology systems
20. Admission blood tests	Haemoglobin (grams / litre) / White cell count (x10 ⁹ / l) / Albumin (grams / litre) / Sodium (mmol/l) / Potassium (mmol/l) / Urea (mmol/l) / Creatinine (ml / min)	– Pathology systems

	*Include the first blood test results from this admission. Only include blood tests taken before surgery	
21. Admission observations	Pulse rate (bpm) / Systolic blood pressure (mmHg) / Glasgow coma scale	–
22. Pre-operative assessment	If elective: Yes (pre-admission anaesthetic assessment clinic) / No. If yes: Did this include pre-operative cardiopulmonary exercise testing (Yes - VO ₂ peak, AT / No). If emergency: Yes (inpatient perioperative or elderly medicine, including physician or nurse specialist) / No	– Clinical letters / notes
23. Preoperative investigations	None / ECG (normal / abnormal) / Echocardiography (LVEF, %) / Coronary angiography	–
Abbreviations: ASA = American Society of Anaesthesiologists; Hb = Haemoglobin; LVEF = Left Ventricular Ejection Fraction PACS = Picture Archiving and Communication.		

Intra-operative Data Fields	Required data (definition / comment)	Suggested source(s)
1. Prior Operations	1 / 2 / >2	
2. Operative urgency (NCEPOD Classification of Intervention)	Immediate (Immediate life, limb or organ-saving intervention - resuscitation simultaneous with intervention. Normally within minutes of decision to operate). Urgent (Intervention for acute onset or clinical deterioration of potentially life-threatening conditions, for those conditions that may threaten the survival of limb or organ, for fixation of many fractures and for relief of pain or other distressing symptoms. Normally within hours of decision to operate) Expedited (requiring early treatment where the condition is not an immediate threat to life, limb or organ survival. Normally within days of decision to operate). Elective (Intervention planned in advance of routine admission to hospital).	– Operative note – Admissions clerking
3. Primary indication	Malignant / Benign If malignant: Primary only / nodal metastases / Distant metastases	– Operative note. – Clinical notes. – Theatre records.
